3.4. STUDY POPULATION

The study will be performed on 108 narcoleptic children to assess the effects of pitolisant compared with placebo in the relief of Excessive Daytime Sleepiness (EDS): children from 6 to less than 12 years of age and adolescents from 12 to less than 18 years of age more or less equally balance between age groups (at least 40%). Each age groups should be also more or less equally balance between genders (at least 40%), all of them suffering from narcolepsy with or without cataplexy.

Patients are allowed to continue their anticataplectic drugs, if they are at stable dosage for at least 4 weeks before the inclusion (V2), and this dosage should be maintained stable throughout the study (from V2 to V8).

The previous use of drug with a psychotropic effect, including psychostimulants for the treatment of EDS should be discontinued at V0 (D-28).

At V1 (D-14), all prohibited treatments should be stopped for at least 14 days.

3.4.1. Inclusion criteria

- 1) Male and female children from 6 to less than 18 years of age (at V8) suffering from narcolepsy with or without cataplexy meeting the International Classification of Sleep Disorders (ICSD-3) criteria (Narcolepsy type 1 and 2). Diagnosis confirmed with polysomnography and Multiple Sleep Latency Test for patients without cataplexy (if these examinations were not performed within the last 12 months)
- 2) PDSS score \geq 15 during baseline period (V1+V2) / 2.

- 3) Patients should be free of non-authorized medication, in particular psychostimulant treatments as from the screening visit (V0) onwards.
- 4) Parents and patients old enough to understand who have expressed a willingness to participate in the study, who have signed and dated the informed consent form prior to beginning protocol required procedures.
- 5) In the opinion of the investigator, the patient must have adequate support to comply with the entire study requirements as described in the protocol (e.g., transportation to and from trial site, self rating scales and diaries completion, drug compliance, scheduled visits, tests).
- 6) Female pubescent patients shall use a birth control method, judged efficient by the investigator, throughout the study and during the month following treatment discontinuation.
- 7) Patients should benefit from appropriate healthy insurance system (only applicable where mandatory e.g. in France).

3.4.2. Non inclusion criteria

- 1) Any other conditions that can be considered the primary causes of EDS: such as sleep related breathing disorders as defined by a sleep Apnea Index ≥ 5 per hour or/and an Apnea/Hypopnea Index ≥ 10 per hour, chronic sleep deprivation, circadian sleep wake rhythm disorder or any other medical or neurological causes that could account for narcolepsy symptoms associated with EDS.
- 2) Cataplectic patients treated by anticataplectics (SNRI, SSRI, sodium oxybate) which are not under a stable treatment since at least 4 weeks at the time of inclusion (V2).
- 3) Patients treated for cataplexy or any other pathology, by tricyclic antidepressants (clomipramine, imipramine, mirtazapine, desmethylimipramine and protriptyline) are not authorized because they display histamine H1 receptor antagonist activity.
- 4) The use of pitolisant within a 30-day period prior to initial screening visit (V0) for this trial.
- 5) Current or recent (within one year) history of a substance abuse or dependence disorder including alcohol abuse as defined in Diagnostic and Statistical Manual of Mental Disorders (DSM-IV).
- 6) Any significant abnormality of the electrocardiogram and particularly Fridericia's QTc interval (OTcF = $OT/3\sqrt{60/HR}$) higher than 450 ms.
- 7) Patients with severe depression (CDI \geq 16).
- 8) Patient with suicidal risk (C-SSRS).
- 9) Positive urinary drug testing (test applicable to patients from 12 years)

EudraCT number: 2013-001506-29

10) Pregnancy (defined as positive β-HCG blood test), breast-feeding, or patients and unable to use an efficient method of birth control shall not be included in the study (for pubescent female only).

- 11) Patients with severe hepatic Impairment (Child Pugh C) or with any other significant abnormality in the physical examination or clinical laboratory results.
- 12) Psychiatric and neurological disorders, such as moderate or severe psychosis or dementia, depression, history of seizure disorder or other problem that, in the investigator's opinion, would preclude the patient's participation and completion of this trial or comprise reliable representation of subjective symptoms.
- 13) Active clinically significant illness, including unstable cardiovascular, endocrine, neoplastic, gastrointestinal, haematological, hepatic, immunologic, metabolic, neurological (other than narcolepsy/cataplexy), pulmonary, and/or renal disease which could interfere with the study conduct or counter-indicate the study treatments or place the patient at risk during the trial or compromise the study objectives.
- 14) Prior severe adverse reactions to CNS stimulants.
- 15) Known hypersensitivity to the tested treatment including active substance and excipients.
- 16) The inability to continue daily activities safely, without the use of treatment against EDS.
- 17) Any patient presenting congenital galactosemia, glucose-galactose malabsorption or lactase deficiency due to the presence of lactose in investigational treatments.
- 18) Patients participating in another study or being in a follow-up period for another study.
- 19) Cannot be contacted in case of emergency.

STUDY TREATMENT

Patients will be outpatients followed in ambulatory way during the whole study period and they will all receive the investigational study treatment pitolisant or placebo as described § 4.2. Patients will be asked to take the study drug every day before breakfast, according to the investigator's prescription regarding the dose regimen of patients, based on the product efficacy

and tolerance.

The total treatment duration of this double blind study is 8 weeks. Patients will start pitolisant treatment with escalating doses scheme on the first 4 weeks, as follows:

- V2 5 mg of BF2.649 or placebo / day during the first week,
 - 10 mg of BF2.649 or placebo /day during the second week,
- V3 Increase to 20 mg/d or maintain at 10 mg/d or reduce to 5 mg/d of BF2.649 (or placebo) per day for 7 days depending on efficacy and tolerability.

- V4 It will also be possible to reduce the dose administered to the patients, or to increase it without exceeding 40 mg/d. Patients with a weight less than 40kg could be treated with a maximum daily dose of 20mg.
- V5 It will be possible to reduce the dose administered to the patients, but not to increase it.
 - As from V5 onwards, no dosage change of the study treatment will be authorized.
- At the end of the double blind treatment (V7), the investigator will provide placebo to all patients for the one-week wash out period.

In open-label period patients will start pitolisant treatment with escalating doses scheme, as follows:

- V8 5 mg of BF2.649 or placebo / day during the first week.
 - 10 mg of BF2.649 or placebo /day during the second week.
- V9 The third week according to investigator prescription and evaluation on efficacy and tolerance, the dose will be maintained or increased at 20 mg/d or reduced at 5 mg/d.
- V10 According to investigator prescription and evaluation on efficacy, tolerance and weight, the dose will be maintained, reduced or increased at 5, 10, 15, 20, 30 or 40 mg/d (only if patient weight is above 40kg) for the next 4-week During the phone contact (T2), in opinion of investigator, the dose could be readjusted according the effectiveness/tolerability of treatment to patient. In case of need, it is possible to plan a visit on site within the week following phone contact for obtaining new bottles of treatment with the corresponding dose.
- V11 According to investigator prescription and evaluation on efficacy, tolerance and weight, the dose will be maintained, reduced or increased at 5, 10, 15, 20, 30 or 40 mg/d (only if patient weight is above 40kg) for the next 3-month.
- V12 According to investigator prescription and evaluation on efficacy, tolerance and weight, the dose will be maintained, reduced or increased at 5, 10, 15, 20, 30 or 40 mg/d (only if patient weight is above 40kg) for the next 6-month.
- All subsequent visits, the treatment dispensation will be done like V12.

3.6. CONCOMITANT TREATMENTS

The investigator must report all concomitant medications in the CRF and record all changes in the dosages during the study.

Protocol P11-06/ BF2.649 EudraCT number: 2013-001506-29

3.6.1. Authorized concomitant treatments

Double-blind period:

If Patients are treated with sodium oxybate, a stable dosage is required for a minimum period of 4 weeks prior to inclusion (V2), and this dosage should be maintained stable

throughout the study.

Other purported anticataplectic treatments e.g. SSRI (fluoxetine, fluoxamine, citalopram,

sertraline, paroxetine) or norepinephrine/serotoninergic uptake inhibitor (venlafaxine),

norepinephrine uptake inhibitors (viloxazine, duloxetine, reboxetine, atomoxetine) are

authorized only if they are maintained at stable dose for a minimum period of 4 weeks prior

to inclusion (V2), and their dose should not be changed throughout the trial.

Antihistamic H1 which do not cross blood brain barrier (BBB) (2nd and 3rd generation).

Any change in the dosage of the other authorized concomitant treatments should be

recorded in the CRF.

Open label period:

Concomitant treatments against EDS and cataplexy such as modafinil, sodium oxybate, methylphenidate or antidepressants (except tricyclics) are authorized. The investigator will be

free to adapt posology.

3.6.2. Prohibited concomitant treatments

Double-blind period:

At V0, all ongoing prohibited treatments are discontinued. At V1, first visit with baseline

assessment, all prohibited treatments should have been stopped for at least 2 weeks.

From screening visit (V0) throughout V8, patients should be free of all other drugs or

substances, namely:

- with a psychotropic effect, including psychostimulants for the treatment of EDS

(amphetamine and amphetamine-like CNS stimulants, methylphenidate or others, such as

modafinil);

- medication with sedating properties (e.g. benzodiazepines, non-benzodiazepine

anxiolytics, hypnotics sedatives, neuroleptics, opioids, antihistaminic products (1st generation),

and anticonvulsants).

Tricyclic antidepressants clomipramine, imipramine, such as Mirtazapine,

desmethylimipramine and protriptyline are not authorized because they display histamine

BIOPROJET Version 3.0 Protocol P11-06/ BF2.649 September 30th, 2020

EudraCT number: 2013-001506-29

H1 receptor antagonist activity and possibly interfere with the effect of pitolisant by

abrogating the effect of endogenous histamine released in brain by pitolisant.

Open label period:

Medication with sedating properties (e.g. benzodiazepines, non-benzodiazepine anxiolytics,

hypnotics sedatives, neuroleptics, opioids, antihistaminic products (1st generation), and

anticonvulsants) are prohibited.

Tricyclic antidepressants such clomipramine, imipramine, mirtazapine, as

desmethylimipramine and protriptyline are not authorized because they display histamine H1

receptor antagonist activity and possibly interfere with the effect of pitolisant by abrogating the

effect of endogenous histamine released in brain by pitolisant.

3.7. EVALUATION CRITERIA

Medical history and demographic data including age, height, weight, gender will be obtained

for each patient screened for entry into the study.

The following measures will be used to assess the safety and efficacy of pitolisant:

3.7.1. Efficacy criteria

3.7.1.1. Primary endpoint: Ullanlinna Narcolepsy Scale score (UNS)

The Ullanlinna Narcolepsy Scale (Appendix 1) is an 11-item scale used to measure the intensity

and frequency of symptoms of narcolepsy (EDS and cataplexy). The first four items address

typical manifestations of cataplexy occurring in situation as laughing, feeling glad or angry or any

exciting situation. The 7 other items measure the sleep latency and the propensity to fall asleep in

various situations. The total score varies from 0 to 44.

The UNS will be evaluated at Visits V1 and V2 (i.e., prior to randomization) as baseline

evaluation and at Visits V6 and V7 (i.e., end of the double-blind treatment period) and reviewed

by the investigator.

The difference of baseline UNS and during the treatment are computed (V1-V2 and V6-V7).

The primary measure of efficacy is based on the change from baseline of the score of the UNS

by comparing the mean of UNS performed at [(V6 + V7)/2] (end of double-blind period) to the

mean of UNS performed at [(V1 + V2)/2] (baseline period). A comparison between pitolisant

and placebo will be made on the score difference between baseline and the end of the treatment

period.

3.7.1.2. Secondary endpoints

3.7.1.2.1. Child and Adolescent Sleepiness Scale (CASS)

In the ESS version adapted for children (6 and over) and adolescents (CASS), this is a simple instrument constituted by 10 items (Sitting and reading, Watching TV, Playing a video or computer game, Playing outside with friends, Travelling in a car or train for longer than one hour, In class during the morning, In class just after lunch, During break time (recess) at school, On Sundays if you lie down for a rest, In the morning when you wake up) each of them scored in 4 categories (Appendix 2). Each of the ten questions is rated from 0 = never, 1 = sometimes, 2 = often to 3 = always (want to sleep). The scores are summarized to yield a score between 0 and 30 with higher scores representing greater sleepiness.

A score greater than 14 is considered as abnormal sleepiness.

CASS will be evaluated at each study visit of double-blind phase and reviewed by the investigator. CASS should be handed out to the patient at approximately the same time of the visit day and with same delay after the investigational treatment intake in order to standardize the possible impact of the treatment on the evaluation.

The patient should be helped in the comprehension of the questionnaire until he/she fully understands the ten questions of the score. It will be reminded to patients, parents, and/or teachers that the CASS measures the subjective sleepiness with regard to the immediate past week.

It occurs frequently that some questions on specific situations are not encountered by the patient in his/her daily life. It is advised to give the patient equivalence to a similar situation in order to have a complete questionnaire filled.

The sum of the rated questions will be made by the investigator and reported in the CRF.

As supportive measure the calculation of responders' rate defined as a reduction of 3 points of the CASS score from baseline or the normalization of the CASS score at 10 or below.

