	of the sample size. At least 96 patients (64 patients being administrated pitolisant, and 32 patients receiving placebo) should be needed for a power of at least 0.75, given the observed values of SD and baseline correlation.
	A new sample size was calculated further the change of the main endpoint and adjustment of the corresponding variability (SD and baseline correlation):
	A difference of at least UNS=3 between the studied treatment and placebo with the observed values of SD and baseline correlation will be detected as significant with a power of 85%, once the sample size is at least 36+72 patients for control and tested drug groups, respectively, thus a total of 108 patients.
Study duration for	Inclusion period 4 weeks (including 2-week baseline period). Followed by, Double-blind period, treated by pitolisant or placebo for 8 weeks,
participants	Followed by, Single blind wash-out period, treated by placebo for 1 week and then Followed by a prolonged open-label period depending on patient wish.
	1) Male and female children from 6 to less than 18 years of age (until V8) suffering from narcolepsy with or without cataplexy - meeting the International Classification of Sleep Disorders (ICSD-3) criteria (narcolepsy type 1 and 2). Diagnosis confirmed with polysomnography and Multiple Sleep Latency Test for patients without cataplexy (if these examinations were not performed within the last 12 months)
	 2) PDSS score ≥ 15 during baseline period (V1+V2) / 2. 3) Patients should be free of non-authorized medication, in particular psychostimulant treatments as from the screening visit (V0) onwards.
Main inclusion criteria	4) Parents – and patients old enough to understand who have expressed a willingness to participate in the study, who have signed and dated the informed consent form prior to beginning protocol required procedures.
	5) In the opinion of the investigator, the patient must have adequate support to comply with the entire study requirements as described in the protocol (e.g., transportation to and from trial site, self rating scales and diaries completion, drug compliance, scheduled visits, tests).
	6) Female pubescent patients shall use a birth control method, judged efficient by the investigator, throughout the study and during the month following treatment discontinuation.
	7) Patients should benefit from appropriate healthy insurance system (only applicable where mandatory e.g. in France).

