# 4.1.5 Derived variables

## 4.1.5.1 General definitions

The following definitions will be considered:

- Analysable value will be defined as any non-missing value.
- Baseline value will be defined as :
  - For UNS, PDSS and CASS parameters as the mean of V1 and V2 values on condition that values are prior to the first IMP intake (*i.e.* before or the same date as the first IMP intake date). In case of a visit missing value, the baseline will be equal to the non-missing value.
  - For other parameters, the last analysable value prior to the first IMP intake (*i.e.* before or the same date as the first IMP intake date).

Note: In case of patient randomised but not treated over the blind period: value at baseline is defined as the last analysable value prior or equal to the date of randomisation.

- Post-baseline value will be defined as any value recorded at a given timepoint after baseline.
- Change from baseline will be defined as the arithmetic difference between a post-baseline value and the baseline value for a given variable at a given time point.
- End value will be defined only for UNS, PDSS and CASS parameters as :

- The mean of V6 and V7 values. In case of a visit missing value, the End value will be equal to the non-missing value.

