# Pediatric Daytime Sleepiness Scale scores (PDSS)

The response to treatment according to PDSS is derived at a visit as a score reduction of 3 Between the baseline and the final value:

- If  $PDSS_B-PDSS_F \ge 3$  then response to treatment at the visit = Yes.
- If PDSSB-PDSSF < 3 then response to treatment at the visit = No.
- Otherwise, response to treatment at the current visit is not calculated.

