#### Analysis:

The difference between placebo and BF2.649 will be studied in the same way as the primary analysis (Excluding sensitivity analysis).

In addition,

 Descriptive statistics at baseline and at each post-baseline visit by treatment group will be provided

Missing data handling:

Missing evaluations are not imputated

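### The protocol's supportive CASS responder rule has no baseline condition on its '10 or below' branch, so a child who enters at 10 or below can count as a responder while unchanged or worse

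*Protocol*

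**What the plan says.** Protocol 3.7.1.2.1 describes ten items that "yield a score between 0 and 30 with higher scores representing greater sleepiness". It then sets an abnormality limit: "A score greater than 14 is considered as abnormal sleepiness". The section ends with a responder rate, introduced by "As supportive measure the calculation of" and "defined as a reduction of 3 points of the CASS score from baseline or the normalization of the CASS score at 10 or below".

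The only sleepiness score used for entry is the PDSS. The main inclusion criteria in the Synopsis require "PDSS score ≥ 15 during baseline period (V1+V2) / 2", and Protocol 3.4.1 repeats this. No inclusion or non-inclusion criterion uses the CASS.

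The SAP handles the CASS as follows:

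- SAP 4.1.5.1 sets the baseline, "For UNS, PDSS and CASS parameters as the mean of V1 and V2 values", and the end value as the mean of V6 and V7.
- SAP 4.1.3.2 leaves the CASS outside the five endpoints tested in sequence, so it is exploratory.
- SAP 4.5.3.3.4 plans the common covariance model ("Excluding sensitivity analysis") and descriptive statistics. It derives no CASS responder.
- For the PDSS, by contrast, SAP 4.1.5.5 has a change-only rule: "The response to treatment according to PDSS is derived at a visit as a score reduction of 3".
- SAP 4.6 lists no modification from the protocol's statistical section.

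**The concern.** A responder should be a child who got better. The two branches are joined by 'or', and the second looks only at the final score. A child who was never above 10 satisfies it by staying there, or even by rising towards 10.

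The word 'normalization' suggests that the child was abnormal before, but the section does not say so, and its own figures do not fit that reading. Abnormal means above 14, yet the target is 10 or below. A child at 11 is not abnormal by the section's definition, but a move from 11 to 10 is counted as normalization.

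At stake is the meaning of a supportive percentage. Some counted successes in both arms would be children with no improvement. The CASS and PDSS responder rates would also follow different logic within one trial. If the CASS rate is produced after unblinding, the analyst would have to choose a reading at that point.

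**Working it through.** **1. No figure to reproduce.** The documents state no CASS responder rate, mean, SD or correlation. The logic can be checked exactly; the frequency only under assumptions.

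**2. Does the entry criterion close the gap?** No. The PDSS has eight items scored 0 to 4. Four of them concern getting up, falling back to sleep, being woken and needing more sleep (Protocol 3.7.1.2.2). Together these can reach 4 × 4 = 16, which already exceeds 15. Nine of the ten CASS items are daytime situations. A PDSS of 15 therefore does not force the CASS above 10, although it makes low values less likely.

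**3. Enumeration.** Let b be the baseline and f the final score, both integers from 0 to 30. The rule as written is: respond if b − f ≥ 3 or f ≤ 10. Responses without improvement have f ≥ b and f ≤ 10, hence b ≤ 10.

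- Unchanged (f = b = 0, …, 10): 11 pairs.
- Worse (0 ≤ b < f ≤ 10): 11 × 10 / 2 = 55 pairs. The largest worsening is 10 points (0 to 10).
- Total: 66 pairs, all with a baseline of 10 or below.

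If the second branch also requires b > 10, the 66 pairs become 0. The only responses left with a fall of less than 3 points are 11 to 10, 11 to 9 and 12 to 10.

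**4. How often, with no drug effect?** Assumed model: baseline and final CASS are bivariate normal with equal means, rounded to half points (each is a two-visit mean) and limited to 0–30; 400,000 simulated pairs per row. The table gives the percentage of all children who are responders with f ≥ b.

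| Mean | SD 4, r 0.5 | SD 4, r 0.7 | SD 5, r 0.5 | SD 5, r 0.7 |
|---|---|---|---|---|
| 14 | 4.0 | 5.2 | 5.7 | 7.2 |
| 16 | 1.2 | 1.8 | 2.4 | 3.4 |
| 18 | 0.3 | 0.5 | 0.9 | 1.4 |

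The range is about 0.3% to 7%. Of 108 children this is 0.003 × 108 ≈ 0.3 to 0.07 × 108 ≈ 7.6.

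**5. What the branch adds in total.** Take mean 16, SD 5, r 0.7. The full rule gives 30.4% responders and the 3-point fall alone gives 23.8%, an increment of 6.6 points. About half of that increment is children who did improve, by less than 3 points. The other 3.4 points are the non-improved children in step 4. Over the whole grid the increment is 1 to 13 points, so it overstates the misclassified share.

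**6. Is the treatment contrast diluted?** I added an assumed 3-point drug effect, with 36 placebo and 72 pitolisant patients and no placebo improvement.

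| Scenario | Rule as written | 3-point fall only |
|---|---|---|
| Mean 16, SD 5, r 0.7 | 30.5 points, power 0.86 | 28.7 points, power 0.83 |
| Mean 14, SD 4, r 0.5 | 31.6 points, power 0.89 | 27.9 points, power 0.81 |

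With effects of 2, 3 or 4 points and no placebo improvement, the rule as written gave the larger difference in all 36 scenarios. The branch also captures treated children who reach 10 or below, and these outweigh the static ones. With a 1-point placebo improvement and a 3-point effect, the order reversed only at mean 14 with r 0.7, and slightly (36.4 v 37.1 points at SD 4; 29.1 v 29.9 at SD 5).

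**The case against.** The strongest reply is that nothing planned depends on this rule. The SAP is the reference for all analyses of the blind part, makes the CASS exploratory and derives no CASS responder. The sleepiness-scale responder rate that it does test is the PDSS one, which is change-only. This stands, and it limits the consequence. It does not settle the matter, because the SAP nowhere says that the CASS rate is dropped. The entry in SAP 4.6 covers the protocol's statistical section, while the responder rule sits among the evaluation criteria, so the protocol wording remains the only definition if the rate is reported.

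Second, 'normalization' in ordinary use means becoming normal, and the form matches the sponsor's adult ESS criterion described in Protocol 1.3 (10 or below, or a 3-point change). A composite rule is a legitimate choice. What remains is that no baseline condition is written, and the mismatch between 10 and 14 prevents a programmer from inferring one.

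Third, the upper end of the range needs a mean CASS of 14, which is not even abnormal by the section's own limit. That looks low for children with narcolepsy, a PDSS of at least 15 and psychostimulants stopped. This is fair. At mean 18 the figure is 0.3% to 1.4%.

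A reader might also infer that the rule weakens the pitolisant-placebo contrast. A simple sum appears to show this. If a share q = 10% sits at 10 or below throughout in both arms, and the others respond at 30% v 60%, the rates become 0.1 + 0.9 × 0.30 = 0.37 and 0.1 + 0.9 × 0.60 = 0.64. The difference falls from 30 to 27 points and power from 0.85 to 0.77. But that sum assumes the dilution, because it fixes the response of everyone else and gives the branch no credit for treated children who reach 10.

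**Conclusion.** The definition is defective as written: it allows a response without improvement in any child who starts at 10 or below, and its cut does not agree with the abnormality limit in the same section. Under the assumed CASS means of 14 to 18, SD 4 to 5 and correlation 0.5 to 0.7, about 0.3% to 7% of all children would be non-improved responders in the absence of any drug effect, inflating the absolute rates in both arms. The real frequency is unknown and may be near the low end.

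Two stronger readings are not supported. The 1 to 13 point increment is not the misclassified share, since about half of it in the worked example is small genuine improvement. General dilution of the treatment difference is not shown either: in most scenarios the rule as written gave the larger difference. The primary UNS analysis and the fixed sequence are unaffected. This is a cheap correction to a supportive measure, best made before unblinding.

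**What to change.** Choose one of three routes.

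- **Keep the composite rule.** Count normalization only when the baseline mean of V1 and V2 is above the normalization cut, and state one cut throughout, reconciling 10 with 14. Requiring a baseline above 14 while leaving the end cut at 10 would make the branch empty: the smallest such fall on the half-point grid is 14.5 − 10 = 4.5, which the 3-point branch already covers.
- **Use change only.** Define response as a fall of at least 3 points from the V1/V2 mean to the V6/V7 mean, the form that the SAP uses for PDSS.
- **Drop the rate.** Say so in SAP 4.6.

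For either of the first two, put the same derivation in Protocol 3.7.1.2.1 and SAP 4.1.5.5, and the reporting in SAP 4.5.3.3.4.

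The cost is wording and one derived variable, with no new data. Responder percentages fall slightly in both arms. The change-only form may also lose a little power on this supportive measure (0.86 to 0.83 in the mean 16, SD 5, r 0.7 example with an assumed 3-point effect).
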